2.1.2 Exclusion Criteria

2.1.2.1 Patients with the following T-cell leukemias/lymphomas: adult T-cell leukemia/lymphoma (ATLL), angioimmunoblastic T-cell lymphoma (AITL), peripheral T-cell lymphoma T follicular helper phenotype (PTCL-TFH), and enteropathy-associated T-cell lymphoma (EATL).

2.1.2.2 Chemotherapy and anti-tumor antibodies within 4 weeks (6 weeks for nitrosoureas or mitomycin C); other tumor-directed systemic therapy and radiation therapy within 2 weeks.

2.1.2.3 Persisting toxicity related to prior therapy of grade > 1 , with the exception of the following: alopecia, sensory neuropathy grade ≤ 2 , or other grade ≤ 2 not constituting a safety risk based on investigator's judgment

2.1.2.4 Patients who are receiving any other investigational agents

2.1.2.5 Patients who have had prior therapy with any antibody/drug targeting PD-1/PD-L1 T-cell coregulatory proteins (immune checkpoints)

2.1.2.6 Current use of immunosuppressive medication, EXCEPT for the following:

- Intranasal, inhaled, topical steroids, or local steroid injection (e.g., intra-articular injection)
- Systemic corticosteroids at physiologic doses ≤ 10 mg/day of prednisone or equivalent; or,
- Steroids as premedication for hypersensitivity reactions (e.g., CT scan premedication)

- 2.1.2.7 Patients with known CNS involvement should be excluded from this clinical trial because of their poor prognosis and because they often develop progressive neurologic dysfunction that would confound the evaluation of neurologic and other adverse events
- 2.1.2.8 Patients with previous malignant disease other than the target malignancy within the last 5 years with the exception of basal or squamous cell carcinoma of the skin or cervical carcinoma in situ
- 2.1.2.9 Patients with history of any organ transplantation, including allogenic stem cell transplantation
- 2.1.2.10 Received a live vaccine within 4 weeks of the first dose of avelumab. Vaccination with a live vaccine while on trial is prohibited. **NOTE:** Seasonal influenza vaccines for injection are generally inactivated flu vaccines and are allowed; however intranasal influenza vaccines (e.g., Flu-Mist®) are live attenuated vaccines, and are not allowed
- 2.1.2.11 Patients with history of allergic reactions attributed to compounds of similar chemical or biologic composition to rhIL-15 or avelumab
- 2.1.2.12 Patients with uncontrolled intercurrent illness including, but not limited to, ongoing or active infection requiring systemic therapy, or psychiatric illness/social situations that would limit compliance with study requirements
- 2.1.2.13 Inability or refusal to practice effective contraception during therapy or the presence of pregnancy or active breastfeeding. Based on its mechanism of action, avelumab can cause fetal harm when administered to a pregnant woman. Animal studies have demonstrated that inhibition of the PD-1/PD-L1 pathway can lead to increased risk of immune-mediated rejection of the developing fetus resulting in fetal death. These potential risks may also apply to other agents used in this study
- 2.1.2.14 Patients with active bacterial infections, documented HIV infection or positive screening serology, PCR evidence for active or chronic hepatitis B or hepatitis C, or positive screening HBV/HCV serology without documentation of successful curative treatment (see Section [12.5](#) for IL-15 administration in HIV positive patients)
- 2.1.2.15 Patients with active or history of any autoimmune disease unrelated to their malignancy, including asthma requiring chronic inhaled or oral corticosteroids, or with history of asthma requiring mechanical ventilation; patients with a history of mild asthma that are on or can be switched to non-corticosteroid bronchodilator regimens are eligible
- 2.1.2.16 Cardiovascular disease: Clinically significant (i.e., active) cardiovascular disease: cerebral vascular accident/stroke (< 6 months prior to enrollment), myocardial infarction (< 6 months prior to enrollment), unstable angina, congestive heart failure (\geq New York Heart Association Classification Class II), or serious cardiac arrhythmia requiring medication
- 2.1.2.17 Other severe acute or chronic medical conditions including immune colitis, inflammatory bowel disease, immune pneumonitis, pulmonary fibrosis or psychiatric conditions including recent (within the past year) or active suicidal ideation or behavior; or laboratory abnormalities that may increase the risk associated with study participation or study treatment administration or may interfere with the interpretation of study results

and, in the judgment of the investigator, would make the patient inappropriate for entry into this study

2.1.3 Recruitment Strategies

Study participants will be recruited from the population of patients screened in the lymphoid malignancies' clinic of the National Institutes of Health. These will include both referrals from outside physicians as well as patient self-referrals. In addition, information will be provided on the ccr.cancer.gov/Lymphoid-Malignancies-Branch and ClinicalTrials.gov web pages. This study will be posted on NIH websites and on NIH social media forums as well as official Lymphoid Malignancy Branch social media accounts. Study-specific public service announcements and informational fliers will be used for recruitment activities. All information to be posted or distributed publicly will be submitted to the IRB for review and approval in advance of use.

2.2 SCREENING EVALUATION

2.2.1 Screening activities performed prior to obtaining informed consent

Minimal risk activities that may be performed before the subject has signed a consent include the following:

- Email, written, in person or telephone communications with prospective subjects
- Review of existing medical records to include H&P, laboratory studies, etc.
- Review of existing MRI, x-ray, or CT images
- Review of existing photographs or videos
- Review of existing pathology specimens/reports from a specimen obtained for diagnostic purposes

2.2.2 Screening activities performed after a consent for screening has been signed

The following activities will be performed only after the subject has signed the consent for study 01C0129, on which screening activities will be performed.

Assessments and procedures to confirm study eligibility should be completed within 28 days prior to registration (unless otherwise noted). See also the Study Calendar provided in Section [3.6](#).

2.2.2 Clinical Evaluations

- Disease history, including: diagnosis, treatment (e.g., systemic treatments, radiation and surgeries), disease status, and significant prior/ongoing side effects and symptoms
- Complete medical history, including: all active conditions considered to be clinically significant by the treating investigator
- Physical examination, including: height (screening only), weight, vital signs (i.e., temperature, pulse, respiratory rate, and blood pressure); review of concomitant medications and symptoms/side effects; and, assessment of performance status

2.2.3 Laboratory Evaluations

NOTE: Results from outside NIH are accepted.

- CBC with differential, platelets and reticulocyte count
- Chemistry panels (as noted) or specific analyte required for eligibility, including: Creatinine (i.e., Acute Care Panel); serum calcium, phosphate, magnesium and albumin (i.e., Mineral Panel); ALT, AST, total and direct (if required) bilirubin (i.e., Hepatic

Panel); 24-hour urine creatinine clearance (if needed to measure CrCl in cases where serum creatinine >1.5mg/dl); and LDH

- Serum Lipase and Amylase
- Coagulation panel, including: PT/INR and a PTT
- Thyroid function tests, including: thyroid stimulating hormone (TSH) with reflex free thyroxine (T4) per DLM policy
- Hepatitis B surface antigen (HBsAg), Hepatitis B core antibody, Hepatitis C antibody (HCV) [qualitative], HIV 1/2 antibody (qualitative) and HTLV-1/2 serologies (within 3 months) **NOTE:** For individuals with a positive hepatitis B core antibody, HBV DNA PCR will be performed to screen for subclinical infection.
- Urinalysis (with microscopic examination if abnormal)
- Antinuclear antibody (ANA), rheumatoid factor (RF) and anti-thyroid antibody
- Creatine phosphokinase (CPK), troponin
- Serum or urine pregnancy test (B-HCG) for women of childbearing potential
- Clonal T-cell receptor rearrangement by PCR

2.2.4 Imaging Studies

NOTE: Results from outside NIH are accepted. Other body areas may be imaged if clinically indicated.

- CT neck, chest, abdomen and pelvis (CT should be performed with IV and PO contrast, unless patient is allergic or has renal insufficiency; other imaging may be substituted at the discretion of the investigator [such as MRI])
- PET/CT torso (extremities to be included if there is confirmed or suspected disease involvement)
- MRI of brain (only in patients with suspected involvement of CNS)

2.2.5 Cardiac Evaluation (within 3 months)

- Electrocardiogram (EKG)
- Transthoracic echocardiogram

2.2.6 Other Procedures

- Pathologic review/confirmation of diagnosis by Laboratory of Pathology, NCI (no time limit). If archival sample is not available, a fresh tumor biopsy and/or peripheral blood sample will be obtained.
- Pulmonary function tests (PFTs): diffusing capacity/alveolar volume (DLCO/VA), forced expiratory volume in 1 second (FEV1) for patients with significant pulmonary or smoking history

2.3 PARTICIPANT REGISTRATION AND STATUS UPDATE PROCEDURES

Registration and status updates (e.g. when a participant is taken off protocol therapy and when a participant is taken off-study) will take place per CCR SOP ADCR-2, CCR Participant Registration & Status Updates found [here](#).

2.3.1 Treatment Assignment Procedures

NOTE: For NCI CCR registration and enrollment system purposes only

2.3.1.1 Cohorts

Number	Name	Description
1	Mature T-cell malignancies: Dose Escalation	Relapsed/refractory T-cell lymphoma other than ATLL, AITL, PTCL-TFH, and EATL (up to 24 evaluable patients)
2	Mature T-cell malignancies: Dose Expansion	Relapsed/refractory T-cell lymphoma other than ATLL, AITL, PTCL-TFH, and EATL (up to 3 additional evaluable patients; 9 total evaluable at the MTD)

2.3.1.2 Arms

Number	Name	Description
1	Experimental Treatment: Dose Escalation	IL-15 by civ infusion at escalating doses of 1, 2, 3 and 4 mcg/kg/day on days 1-5 of each 28-day cycle (max 6 cycles) with avelumab by IV infusion at a dose of 10mcg/kg on Day 8 and 22 of each cycle, to determine MTD
2	Experimental Treatment: Dose Expansion	IL-15 by civ infusion at the MTD on days 1-5 of cycles 1-6 with avelumab at 10mcg/kg on Day 8 and 22 of each cycle

2.3.1.3 Randomization and Assignment

Treatment assignment is open-label, and non-randomized/non-stratified. Subjects in Cohort 1 are directly assigned to Arm 1; subjects in Cohort 2 are directly assigned to Arm 2.

2.4 BASELINE EVALUATION

The following should be performed within 28 days prior to the first dose of rhIL-15 unless otherwise noted; tests performed as part of screening do not need to be repeated if they were performed within the specified window prior to initiating treatment.

2.4.1 Clinical Evaluations

- Medical history (interim)
- Physical examination including weight, vital signs (i.e., temperature, pulse, respiratory rate, and blood pressure); review of concomitant medications and symptoms/side effects; and assessment of performance status (ECOG performance score, see [APPENDIX A](#)).

2.4.2 Laboratory Evaluations

NOTE: Results from outside NIH are accepted

- Required within 7 days:
 - Serum or urine pregnancy test (B-HCG) for women of childbearing potential
- Required within 14 days:
 - CBC with differential, platelets and reticulocyte count
 - Chemistry panels including: Acute Care (sodium, potassium, chloride, CO₂, glucose, BUN, creatinine), Mineral Panel (serum calcium, phosphate,

magnesium and albumin), Hepatic Panel (alkaline phosphatase, ALT, AST, total and direct bilirubin), and 24-hour urine creatinine clearance (if needed measure CrCl if serum creatinine >1.5mg/dl)

- Others: LDH, Uric acid, Total protein
- Coagulation panel, including: PT/INR and aPTT
- Iron panel (includes: ferritin, transferrin, iron), folate, vitamin B12
- C-reactive protein (CRP)
- Serum Lipase and Amylase
- TSH with reflex free T4
- Urinalysis (with microscopic examination if abnormal)
- HLA typing (A, B, C, DR, DQ)
- Soluble IL-2R
- Creatinine phosphokinase (CPK), troponin I

- Required within 28 days:
 - Lymphocyte Phenotype: T, B and NK cell subsets
 - Antinuclear antibody (ANA), rheumatoid factor (RF) and anti-thyroid antibody

2.4.3 Imaging Studies

Every participant should have an evaluation of known sites of disease as part of baseline evaluation. **NOTE:** Only results from NIH are accepted

- One or more of the following studies: CT, MRI, FDG-PET and/or clinical photography
- Patients with neurological symptoms or signs should undergo MRI scan* of the brain and lumbar puncture

*NOTE: The MRIs to be done in this study may involve the use of the contrast agent gadolinium, if clinically indicated. The risks associated with MRIs and contrast are discussed in the consent form.

2.4.4 Other Procedures

- Bone marrow biopsy and aspiration to assess lymphoma involvement (within 3 months)
- Selected patients with cutaneous disease (as determined by physician PI or AI) will have clinical photography and dermatology assessment performed to assess their skin disease

2.4.5 Research Correlates

NOTE: See Section 5 for additional information. The following sample types will be collected for correlative research studies:

[figure not shown]
- Required:
 - Blood samples for lymphocyte subset testing and circulating tumor DNA
 - Blood, buccal swab, or saliva for germline DNA
 - Tumor Tissue (archival or fresh)

- Optional:
 - Blood samples for ADCC of avelumab, tissue immune cell subset comparison (as outlined in Section 5.1)
 - Bone marrow biopsy
 - Tumor biopsy is required if archival tissue is not available or adequate; otherwise, this is optional.

3 STUDY IMPLEMENTATION

3.1 STUDY DESIGN

In patients with relapsed or refractory T-cell malignancies, IL-15 will be administered by continuous intravenous infusion in a dose-escalation 3 + 3 system with a starting dose of 1 mcg/kg/day, a second dose level of 2 mcg/kg/day, a third dose level at 3 mcg/kg/day, and a fourth dose level at 4 mcg/kg/day on days 1-5 of each of six cycles. Avelumab (IV over 1 hour) will be administered at a dose of 10 mg/kg on days 8 and 22 of the cycle. Treatment will continue for a maximum of 6 cycles or until toxicity (i.e., dose limiting toxicity as found in Section 3.1.1 or toxicity requiring hold as defined in Section 3.3) or progressive disease.

3.1.1 Dose-Limiting Toxicity

A dose-limiting toxicity (DLT) is defined as: any grade 3, 4, or 5 toxicity if not incontrovertibly due to disease progression or an extraneous cause, and deemed possibly, probably or definitely related to IL-15 or avelumab by the PI or designee during the first 28 days of treatment, with the following exceptions.:

3.1.1.1 Hematologic exceptions

- Grade 3 or 4 lymphocytopenia without clinical signs of infection grade 2 or above.
 - rhIL-15 and avelumab will be continued in the event of asymptomatic grade 3 or 4 lymphocytopenia, unless there are clinical signs of significant infection (persistent fevers, labile blood pressure, localized complaints or findings on physical examination, hypoxia or organ dysfunction).
- Grade 3 or 4 neutropenia without clinical signs of infection grade 2 or above.
 - rhIL-15 and avelumab will be continued in the event of grade 3 neutropenia unless there are clinical signs of significant infection, as listed above.
- Grade 3 leukocytosis (WBC > 100,000/mm3) in the absence of signs of leukostasis or other toxicities possibly related to the expansion of activated cells

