3.1.1.2 Non-Hematologic exceptions

- Transient (< 24 hours) grade 3 hypoalbuminemia, hypokalemia, hypomagnesemia, hyponatremia or hypophosphatemia which responds to medical intervention. rhIL-15 and avelumab will be continued while the metabolic abnormalities are corrected by intravenous or oral supplementation
- Non-sustained (< 7 days) grade 3 liver function test (ATL, AST, alkaline phosphatase, total or direct bilirubin) abnormalities deemed unrelated or unlikely related to avelumab, in the absence of clinical signs of hepatic dysfunction (lethargy, confusion, anorexia, pruritus, tremor); for patients with baseline grade 1 elevations, any increase $\geq 10 \times$ baseline will be considered dose-limiting and these patients will be closely monitored for liver function abnormalities. rhIL-15 and avelumab will be continued as long as these abnormalities do not persist for more than 7 days or the patient does not exhibit findings consistent with hepatic toxicity

Management and dose modifications associated with the above adverse events are outlined in Section 3.3. Occurrence of any DLT-defining toxicity after the first 28 days of treatment will lead to permanent discontinuation of protocol therapy; however, will not be deemed a DLT for purposes of dose escalation.

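### Infection-free Grade 3-4 lymphocytopenia and neutropenia are exempt from the DLT rule but a low total white count is not, so the same blood sample can be both exempt and dose-limiting

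*Combined protocol and SAP*

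**What the plan says.** Section 3.1.1 sets a broad rule: a DLT is "any grade 3, 4, or 5 toxicity if not incontrovertibly due to disease progression or an extraneous cause", provided the principal investigator or designee judges it at least possibly related to either drug and it falls in the first 28 days. Only listed exceptions escape.

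Section 3.1.1.1 lists three hematologic exceptions:

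- "Grade 3 or 4 lymphocytopenia without clinical signs of infection grade 2 or above", with the instruction that "rhIL-15 and avelumab will be continued in the event of asymptomatic grade 3 or 4 lymphocytopenia" unless there are signs of significant infection.
- "Grade 3 or 4 neutropenia without clinical signs of infection grade 2 or above", with the instruction that "rhIL-15 and avelumab will be continued in the event of grade 3 neutropenia unless there are clinical signs of significant infection". Grade 4 neutropenia has the DLT exception but no instruction to continue.
- "Grade 3 leukocytosis (WBC > 100,000/mm3) in the absence of signs of leukostasis" or of other toxicities from expanding activated cells. This is the only exception that concerns the total white count, and it concerns a high count.

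A DLT also ends treatment. Section 3.1 continues therapy "until toxicity (i.e., dose limiting toxicity as found in Section 3.1.1" or other specified events, and Section 3.8.1 lists the Section 3.1.1 toxicities among the reasons for removal. For later cycles, Section 3.1.1.2 states: "Occurrence of any DLT-defining toxicity after the first 28 days of treatment will lead to permanent discontinuation of protocol therapy". Those late events do not count toward escalation.

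**The concern.** The rhIL-15 adverse event list in Section 14.1.8 carries *White blood cell decreased* as its own CTCAE 5.0 term, apart from the lymphocyte and neutrophil terms. It is therefore gradable separately, and its place on a possible-relationship list makes the relatedness test easy to meet. Yet the total is the sum of the cell lines. A blood count with differential reports all of them from one tube, so the plan can call the components acceptable and their sum dose-limiting.

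Two things are at stake. First, the DLT count determines the MTD, and the error runs toward a lower MTD. Second, a patient with relapsed or refractory lymphoma could lose therapy over counts the plan elsewhere accepts. A team that sensibly lets the cell-line exception govern avoids both outcomes, but is then not applying the DLT rule as written.

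**Working it through.** **The provisions side by side, for one infection-free sample with Grade 3-4 lymphocytes and a related Grade 3 total white count**

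| Item | Provision | Result |
|---|---|---|
| Lymphocytes | 3.1.1.1, first exception | Not a DLT; continue both drugs if asymptomatic |
| Neutrophils, if Grade 3 | 3.1.1.1, second exception | Not a DLT; continue both drugs |
| Neutrophils, if Grade 4 | 3.1.1.1, second exception | Not a DLT; no continue instruction |
| Total white count, low | 3.1.1, no exception found | DLT; stop (3.1, 3.8.1) |
| The same low total after Day 28 | 3.1.1.2 | Permanent discontinuation; not counted for escalation |

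With Grade 4 neutropenia alone, the conflict is confined to DLT counting. With lymphocytopenia or Grade 3 neutropenia it extends to whether treatment continues.

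**Can a low total arise without Grade 4 neutropenia?** The protocol gives no cut-offs for low counts, so those below are assumptions. Total = neutrophils + lymphocytes + other white cells. Take neutrophils 1,050/mcL (just above the entry floor of 1,000 in Section 2.1.1.7), lymphocytes 150, and other cells 100 to 500:

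1,050 + 150 + (100 to 500) = 1,300 to 1,700/mcL.

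If a total below *c* is Grade 3 or worse, the condition is other cells < *c* − 1,200:

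| Assumed *c* | Other cells must be below | Share of the 100-500 range |
|---|---|---|
| 1,300 | 100 | none |
| 1,500 | 300 | lower half |
| 1,700 | 500 | all but the top value |
| 2,000 | 800 | all |
| 2,500 | 1,300 | all |

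Lymphocytes of 150 are Grade 3-4 for any assumed Grade 3 cut-off from 200 to 500. A patient entering at both floors of Section 2.1.1.7 (lymphocytes 500, neutrophils 1,001) has a total of 1,001 + 500 + (100 to 500) = 1,601 to 2,001. That section sets no floor for the total, so eligibility too handles low white counts by cell line.

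No overlap of the two drugs' toxicities is needed. Section 12.4 expects none, but it reports lymphopenia during infusion in the continuous intravenous IL-15 trial, so rhIL-15 alone can lower an exempt line.

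**The plan's own figure.** The escalation table in Section 10.2 follows from P(escalate) = (1−p)³ + 3p(1−p)² × (1−p)³.

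| True DLT rate p | 10% | 20% | 30% | 40% | 50% | 60% |
|---|---|---|---|---|---|---|
| Stated | 0.91 | 0.71 | 0.49 | 0.31 | 0.17 | 0.08 |
| Recomputed | 0.906 | 0.709 | 0.494 | 0.309 | 0.172 | 0.082 |

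The table is right for whatever p the DLT definition produces. A wider definition raises p and lowers P(escalate). By how much depends on how often the event occurs, and Section 14.1.8 gives no frequencies, so I stop there.

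**What the plan does fix.** Under Table 3 in Section 3.1.2:

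- One such event among the first three patients, with no other DLT, requires three more at that level. That is 3/30 = 10% of the accrual ceiling, and 3/2 = 1.5 to 3/1 = 3 months at the stated 1-2 patients a month, plus the 28-day DLT window.
- These patients stay within the planned maximum of 4 × 6 + 3 = 27 evaluable.
- Two such events at a level, or one plus a DLT in another patient there, stop escalation.

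**The case against.** The best counter-argument is Section 6.1.2.1, under which an abnormal laboratory value is an adverse event only if it brings symptoms, treatment, discontinuation, a serious event or judged clinical impact. On that view an asymptomatic low total would usually never be recorded. This narrows the gap without closing it. That section governs data recording and does not mention DLTs. Section 3.1.1.1 has to deal expressly with asymptomatic lymphocytopenia, so bare laboratory grades were evidently expected to count. Discontinuation as a criterion is also circular here.

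A second argument is that no sensible team would exempt a lymphocyte fall and then count it again through the total. That may well describe practice, but Section 3.1.1.2 names excepted electrolytes and liver tests one by one, which favors reading an unnamed term as not excepted.

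Third, timing. Section 12.4 places lymphopenia only during infusion (Days 1-5 here), and the scheduled Cycle 1 blood counts in Section 3.6, as far as the table can be read, may mostly miss the low point. This reduces how often the event would be seen. Week 1 of Cycle 1 is inpatient, however, and Section 3.6 allows further tests when clinically indicated.

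Fourth, anemia and thrombocytopenia are also unexcepted, so strictness could be deliberate. But neither is a sum of exempt components. If strictness on the total is intended, the plan needs to say which instruction prevails.

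It also stands that the frequency is unknown, that the illustration rests on assumed counts and cut-offs, that the extra patients and months would follow from any single DLT, and that the error is conservative for safety.

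**Conclusion.** The concern holds. Followed as written, the DLT rule counts a low total white count made up of cell lines the plan has already accepted, and gives opposing instructions on continuing treatment. Each occurrence can cost three extra patients (10% of the ceiling, 1.5 to 3 months of accrual) or help stop escalation early, and can remove a patient from therapy.

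This rests on the total reaching Grade 3 or higher, being judged at least possibly related, and being treated as a toxicity despite Section 6.1.2.1. The occurrence rate is not in the documents and may be zero, so no shift in the MTD or in escalation probability is asserted. My confidence is medium. The point should be fixed because the rule feeds a primary endpoint and is better settled before a case arises than mid-cohort.

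**What to change.** Add one bullet to Section 3.1.1.1: *Grade 3 or 4 white blood cell decreased (leukopenia) with no clinical signs of an infection of Grade 2 or higher. Whether rhIL-15 and avelumab continue is decided by the lymphocytopenia and neutropenia instructions above.* The second sentence leaves the present handling of Grade 4 neutropenia unchanged.

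If the sponsor wants leukopenia to be dose-limiting, state instead that it overrides the two cell-line exceptions.

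The cost of the new bullet is one line of text, with no added tests or patients. The downside is that slightly fewer events count as DLTs, limited to infection-free low white counts.
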